Adoption will be assessed via usage metrics from the BrightOutcome platform (e.g., mean % of pages viewed, number of skills and practice exercises used). During post-intervention assessment, we also will ask participants to complete a checklist of reasons for non-adherence (e.g., not enough time, lost interest, forgot).

Patient-reported outcomes will be collected at baseline and post-intervention via REDCap, using the 4-item Perceived Stress Scale, along with PROMIS computer adaptive tests (CATs) of anxiety, positive affect, meaning and purpose, depression, and sleep disturbance. The Differential Emotions Scale (DES) will be administered daily throughout the ALDER intervention on the BrightOutcome website.⁵⁵⁻⁶⁰ Demographics (e.g., gender, race, age) will be collected at baseline to characterize the sample and examine potential moderators.

BZRA usage, symptoms, and attitudes: Participants will self-report the name of BZRA(s) they use, frequency of use (# per week), and reasons for using (anxiety, sleep, stress, other). To measure attitudes towards BZRA use, we will also administer the revised Patients' Attitudes towards Deprescribing questionnaire for benzodiazepine receptor agonists (rPATD-BZRA). In accord with safety monitoring (see those sections below), we also will administer weekly the Benzodiazepine Withdrawal Symptom Questionnaire (BWSQ).

Clinical variables will be abstracted from the electronic health record via EDW reports. These will include rate of BZRA usage (total dose/days to refill, measured up to 3 months post-intervention), along with

covariates and adverse events (e.g., , medication list, falls, withdrawal). Participants will also complete the self-administered comorbidity questionnaire at baseline.

Aim 3: Interviews

We will conduct follow-up interviews with Aim 2 pilot participants (up to n=40 older adults) and with up to 20 clinic staff who provide care to patients who take BZRAs. Interview procedures will be like those in Aim 1 (e.g., conducted remotely, de-identified transcripts, \$100 compensation). Semi-structured

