(5-6) In the event that a participant contacts the study directly to report severe distress or suicidality, or reveals this information online in an email or via the ALDER platform, the project director or a study team member will immediately alert the clinical psychologist ([name]) so that PD and [name] are immediately aware. [name] and the PD will work together to assess the situation and take immediate, appropriate steps. Designated research staff will promptly respond to a distressed participant with appropriate information about how to seek help. In previous studies, we have developed monitoring plans for responding to signs of distress in eHealth trials; an updated version of this protocol, tailored for the ALDER pilot trial, is included in the eIRB materials for this project. Based on our past experience conducting online studies with similar features (e.g., LEAF, LARKSPUR, MARIGOLD), the risk of these occurrences is minimal and the study team is well versed in handling/managing these instances, if they happen. In addition, within REDCap, we have set automatic flags to monitor responses to the following item within the PROMIS CAT for depression, "I felt I had no reason for living." Because we are using the CAT administration of this measure, not all participants will be asked to respond to this item. For those who do receive this item as part of the PROMIS depression CAT, any response more than "Never" (i.e., rarely, sometimes, often, or always) will be flagged within REDCap and will automatically trigger an email notification to the study team, who will then follow the attached safety protocol (see "template telephone response for possible SI").

(7) For Aim 2 participants who may decide, in conjunction with their healthcare clinician, to decrease their use of benzodiazepine receptor agonist (BZRA) medications, risks include symptoms such as gastrointestinal symptoms, tinnitus, sensory hypersensitivity, muscle twitches, perceptual disturbances, hallucinations, depersonalization, cognitive impairment. Research has demonstrated that the risks of symptoms worsening during deprescribing are small and are usually mild and short-term insomnia, anxiety, and restlessness⁶⁵. As ALDER does not involve directly deprescribing BZRAs to patients, these are standard of care risks for patients who wish to decrease their use of BZRAs, whether or not they choose

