to participate in the study. Risks will be minimized by weekly monitoring and reporting of elevated withdrawal scores to the prescribing clinician. Standard guidelines for tapering of benzodiazepines recommend a slow taper, targeting a dose reduction of benzodiazepines no faster than a 25% reduction every 2 weeks and no more than 10% per week. As withdrawal symptoms may increase as patients approach the end of the taper (i.e., reach around 25% of their original dose), standard guidelines suggest decreasing the dosage at this point by no more than 10% every 2 weeks. While these are the standard guidelines for deprescribing BZRs, patients will work with their prescribing clinician to decide on a schedule that best fits their healthcare goals. Therefore, each patient's individual tapering schedule may differ from the one outlined above. To monitor for risks of withdrawal, we will administer the Benzodiazepine Withdrawal Symptom Questionnaire (BWSQ) weekly. If the patient has a BWSQ score of greater than 20 points, 2 or more severe symptoms, or endorses hallucinations, we will contact the patient and their prescriber to facilitate clinical follow-up with the patient's existing healthcare clinician.

Safety risk reporting and action plan. Any participant in need of treatment due to distress will be referred for appropriate services by study staff. In severe cases, the PI will be informed immediately. The study staff will report breach of confidentiality risks incurred by participants to the PI. The PI will be responsible for informing the IRBs and the Project Officer immediately of any life-threatening incidents (although this risk is very low and not expected to happen). The PI will take appropriate action to stop the study, release a participant from the study, or modify procedures to reduce and/or eliminate the occurrence of the abovementioned risks occurring at an unacceptable level.

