Adverse events. All adverse events will be tracked and the PI informed within 24 hours to assess the situation and follow-up. An adverse event form will be developed detailing the problem, actions taken, supervisor notes, and follow-up steps performed. The form, supplemented by regular session notes will be immediately sent to appropriate agencies, including the IRB and US Deprescribing Research Network (USDeN). Any action recommended by one of the IRBs will be conveyed to the USDeN. The PI will be responsible for the monitoring and reporting of any adverse events. The co-investigators will be consulted as appropriate.

All problems having to do with subject safety will be reported by the Principal Investigator to the IRB within ten working days. Specifically, the following will be reported, in writing:

1) all serious adverse events associated with the study procedures, and/or 2) any incidents or problems involving the conduct of the study or participation, including problems with the recruitment and/or consent processes. The Principal Investigator will provide a discussion of any problems noticed during each year in the course of the study to the IRB and USDeN on an annual basis.

If, during the course of communicating with study staff (e.g., synchronously on phone/video or asynchronously via email), a participant indicates severe elevation of distress or possible suicidal ideation, study staff will follow the attached Safety Protocol, which has been developed by [name] (PI and licensed clinical psychologist), based on procedures used in their prior studies of positive emotion skills delivered online. Staff who are responsible for communicating directly with participants will be trained on the Safety Protocol by [name]. Trainees will be responsible for reading the entire Safety Protocol prior to training. Then training will include: a discussion/review of all elements of the Safety

Protocol; time for all trainees to discuss any relevant experience and ask questions; and the opportunity to role play using the telephone template responses.

20.0 Long-term Data and Specimen Storage and Sharing:

- Pre-screener and consent data will be collected and housed via REDCap at Northwestern University.

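### Record reports are the only described systematic source for falls and other medical adverse events, so events that leave no record are missed unless volunteered

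*Combined protocol and SAP*

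**What the plan says.** Section 8.0 (Measures, clinical variables) names one source: "Clinical variables will be abstracted from the electronic health record via EDW reports". The items to be taken from it are the rate of BZRA usage, with "covariates and adverse events (e.g., , medication list, falls, withdrawal" listed alongside. The only time window in that sentence, "measured up to 3 months post-intervention", sits inside the bracket that defines the BZRA usage rate. No window is given for adverse events, and no frequency is given for the reports.

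Some harms are asked of participants directly. For withdrawal, "we also will administer weekly the Benzodiazepine Withdrawal Symptom Questionnaire (BWSQ", and Section 19.0 sets contact triggers that begin "If the patient has a BWSQ score of greater than 20 points, 2 or more severe symptoms, or endorses hallucinations". For suicidality, a response other than the lowest on one PROMIS depression item "will be flagged within REDCap and will automatically trigger an email notification to the study team". Because the scale is adaptive, not everyone receives that item. Unprompted reports of distress also have a route: "In the event that a participant contacts the study directly to report severe distress or suicidality", the study's clinical psychologist is alerted.

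On adverse events in general, Section 19.0 promises: "All adverse events will be tracked and the PI informed within 24 hours to assess the situation and follow-up". The form for recording them is still to be developed.

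**The concern.** Participants are 65 or older and report taking a BZRA at least twice a week (Section 2.0). Section 1.0 itself describes these drugs as especially risky at that age. All procedures can be done remotely (Section 5.0), so no visit is planned at which staff would notice an injury. Falls are an obvious event to count in this population, and the protocol names them, yet the described way of finding them depends on the event reaching a health record. A fall that leads to no care contact reaches none.

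Two things are at stake. The first is the safety information carried forward from the pilot, since Aim 3 is to design a hybrid implementation-effectiveness trial. A low fall count could reflect the data source as much as the participants. The second is how soon the PI learns of a medical event that only a record report would reveal.

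**Working it through.** **1. The plan's own figures.** The plan gives no figure for adverse events. Its only statistical figures are the 95% interval half-widths in Section 3.0, and they reproduce with the normal formula:
- n = 40: 1.96/√40 = 0.310 SD for a mean; 1.96 × 0.5/√40 = 15.5% for a proportion.
- 20% attrition, n = 32: 1.96/√32 = 0.346 SD; 1.96 × 0.5/√32 = 17.3%.

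These describe sampling error only. They say nothing about events that were never recorded.

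**2. Which sources would reveal a fall, injury, emergency visit or hospital stay?**

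| Source described | Timing | Described as asking about such events? |
|---|---|---|
| Perceived Stress Scale, PROMIS scales | Baseline and post-intervention | No |
| Acceptability items, checklist of reasons for non-adherence | Post-intervention | No |
| Comorbidity questionnaire | Baseline | No |
| BZRA name, frequency and reasons for use; attitudes questionnaire | Timing not stated separately | No |
| Differential Emotions Scale | Daily during the intervention | No |
| BWSQ | Weekly | Withdrawal symptoms only |
| Flagged PROMIS item | With the depression scale, if presented | Suicidality only |
| Staff check of the website | Weekly | No question put |
| Adverse event form | Still to be developed | Documents a known event; no schedule for asking |
| EDW reports | Frequency not stated | Yes, if the event is in the record |

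The seven safety risks listed in Section 19.0 do not include falls, and the monitoring procedures there follow that list.

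**3. Direction and size of the bias.** Let *p* be the probability that a participant has at least one fall, and *s* the share of fallers whose fall is in the EDW. With 40 participants, 40*p* fallers are expected and 40*ps* are recorded, so the recorded fraction is *s*. If a share *v* of the unrecorded fallers volunteer the event, the fraction becomes *s* + *v*(1 − *s*), which stays below 1 unless every one of them does. The direction is therefore fixed. The size is not, because the documents give none of *p*, *s* or *v*.

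Purely to show the sensitivity, assume *p* = 5% to 20%, *s* = 25% to 75% and *v* = 0. The chance of recording no faller is (1 − *ps*)^40.

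| Assumed *p* | Assumed *s* | Expected fallers | Expected recorded | P(none recorded) | P(none) at full capture |
|---|---|---|---|---|---|
| 5% | 25% | 2 | 0.5 | 60.5% | 12.9% |
| 10% | 50% | 4 | 2 | 12.9% | 1.5% |
| 20% | 75% | 8 | 6 | 0.2% | below 0.1% |

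The distortion runs from small to large over plausible-looking inputs, so no single figure should be cited.

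**4. The 24-hour notice.** Section 19.0 does not say when the 24 hours start.
- If they start when staff become aware, an event found in a report can be notified within 24 hours of being read. The plan sets no limit on the time from event to report.
- If they start at the event, a report with no stated schedule gives no assurance. Neither does a weekly questionnaire or a weekly website check, which can surface an event up to seven days later.

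On either reading, timely notice of an event known only from the EDW is not assured.

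**The case against.** The strongest reply has four parts.

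- **Harms are asked about.** A reader might infer that adverse events in general have no participant question. The documents do not support that: withdrawal, listed next to falls in Section 8.0, is asked weekly with defined triggers, and suicidality has a flagged item for those who receive it. The point is limited to falls and other medical events.
- **The 24-hour promise is not contradicted.** A reader might infer that it is bound to fail. With a clock that starts at staff awareness it can be kept to the letter. A reader might also take the three-month window as the schedule for adverse event reports, but it qualifies BZRA usage only. What stands is that the report schedule and the clock start are missing.
- **The forms are not in the documents.** The survey forms and the Safety Protocol are separate materials, and the adverse event form is yet to be written. A falls question there cannot be ruled out. Participants also have staff contact details and may report an event unprompted. If such a question exists, the plan should name it and give its timing.
- **The consequence is limited.** Aim 2 estimates feasibility, acceptability and adoption. The study does not itself deprescribe, its procedures are described as minimal risk, and the statistical section plans no safety analysis. No progression rule uses a fall count. This argues for proportion, and the remedy is proportionate. The plan still undertakes to track every adverse event, and its described source cannot do so for unrecorded, unvolunteered falls.

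That the EDW holds only Northwestern encounters is an inference from its description in Section 4.0. The point does not depend on it, because a fall with no care contact is in no health record.

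**Conclusion.** The point holds for falls and other medical adverse events: injuries, emergency visits and hospital stays. EDW reports are their only described systematic source, no described measure asks participants about them, and those that leave no record there are missed unless volunteered. The count is biased low by an amount that the documents do not allow one to calculate; the figures in the working rest on assumed fall risk and capture. For events found only through the EDW, prompt notice to the PI is not assured, because the report frequency and the start of the 24-hour clock are unstated. This rests on the measures as described in Sections 8.0 and 19.0 and would fall away if the unseen forms already contain a suitable question. It is a gap that should be closed; it does not undermine the pilot's feasibility aims.

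**What to change.** - Add one question to each weekly BWSQ administration and to the week-8 survey: any fall, injury, emergency visit or hospital stay since the last form.
- Let a positive answer alert study staff and start the 24-hour notice to the PI. The protocol does not say which platform carries the weekly BWSQ, and Section 20.0 describes REDCap assessments at two time points only. The alert should be built on whichever platform is used; the existing REDCap flag is a model but may not transfer directly.
- State in Section 19.0 that the 24 hours run from staff awareness.
- Keep the EDW as a secondary source, and state its report frequency and its window for adverse events.
- Report events as self-reported, EHR-recorded, and either.

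The cost is one question on forms already being sent and one more alert to set up. The downsides are slightly more participant burden, more minor events for staff to log and a less favourable adverse-event count.

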9.0 Research with Vulnerable Populations

N/A

10.0 Incomplete Disclosure or Deception:

N/A

11.0 Consent Process:

Online consent for all aims will be taken through a REDCap electronic consent form. Participants will be given time to read through the consent form and call or email study staff with any questions before they choose to consent or deny. Participants will consent electronically by entering the date and by typing their full name into the form, which will represent their electronic signature. Participants will be considered “consented” only if they provide both items (date and electronic signature). Consent will be time-stamped and participants will be able to save, download, and/or print a copy of the consent form for their records. Participants may also email the project director to request a copy of the consent form at any time.

We have included the language for the Certificate of Confidentiality and HIPAA Authorization, which explains the information we will be accessing from the Electronic Health Record, only for the purposes of the study and only for a specific amount of time. A partial HIPAA waiver is requested for Aim 1 for recruitment purposes.

Participants can consent to be contacted for future studies.

The online consent forms for Aims 1 and 2 have been uploaded with this submission. Clinician consent form for Aim 3 will be uploaded for IRB review prior to initiating that phase of the project. Because the Aim 2 consent form will include Aim 3 procedures, a separate consent for Aim 3 is not required for patients enrolled in the trial. However, a separate consent for Aim 3 clinic staff is provided.

If a participant chooses to withdraw during the study, their data will be retained up until their point of withdrawal. When a participant withdraws, they will no longer receive future assessments and they will no longer receive daily reminders to log-in to the website.

12.0 Waiver of Participant Signature on Consent Form:

N/A

13.0 Waivers and Alterations of Consent Information:

N/A

14.0 Financial Compensation:

Aim 1 and Aim 3 interview and focus group participants will be compensated \$100 via a gift card. They will be sent their compensation following their participation in an interview or focus group.

Aim 2 participants will receive a \$50 gift card following the completion of their post-intervention assessment.

15.0 Audio/Video Recording/Photography

Interviews and focus groups will be conducted on Zoom and audio recorded. Once recorded, the audio files will be transferred to a secure and password-protected server (NU Sharepoint) and will only be accessible to IRB approved research staff. All other copies of the recording will be deleted. The audio files will then be transcribed and deleted.

The transcripts will be fully deidentified and kept on NU Sharepoint. They will be organized, managed, and processed for analysis in Dedoose.⁶¹ Qualitative analysts (Drs. [name], [name], TBN postdoc) will analyze transcripts using a rapid qualitative synthesis approach⁶² that captures “what works” (Plus), “what needs to be changed” (Delta), and additional insights. Final categories will be determined based on group discussion, including with the stakeholder panel. Findings from Aim 1 will be used to adapt ALDER intervention content and implementation strategies, which will be documented, respectively, using the Framework for Reporting Adaptations and Modifications-Enhanced (FRAME) and FRAME-Implementation Strategies (FRAME-IS),^{63,64} and reported according to criteria for rigor in qualitative research. Results from Aim 3 will be interpreted with guidance from the stakeholder panel and used to inform future directions.

16.0 Potential Benefits of this Research:

There is no guaranteed benefit from participating in ALDER; however, participants might enjoy the skills taught in ALDER and continue practicing them beyond the online course (e.g., keeping a gratitude journal, completing everyday chores mindfully, or listening to a breath awareness meditation recording). Participants may gain mindfulness skills, regularly capitalize on positive events, or use positive reappraisal to reassess daily stressors. Even after completing the course, participants are encouraged to keep using their favorite skills, whether formally through the website and/or journaling about their experiences, or informally in their everyday lives. We hypothesize that participants in the ALDER pilot trial will experience increased positive emotions and decreased distress, anxiety and sleep disturbance. Results from this study may clarify a successful approach to integrating an online positive emotion intervention into clinical care aimed at managing symptoms such as anxiety and supporting BZRA deprescribing.

17.0 Potential Risks to Participants:

Possible discomfort while interacting with the ALDER platform

ALDER is relatively easy to administer and is a low-cost intervention. A potential risk of discomfort might arise with participants who do not have extensive experience using the internet, a tablet/computer, or mobile device. Participants might experience frustration or delayed onboarding if they are less familiar with using computer applications, browsing the internet, or connecting to wireless internet. The ALDER BrightOutcome website will be optimized for mobile use to minimize frustration when accessing the website on a smartphone. Participants will be able to contact IRB-approved study staff for technical support, if needed.

Possible discomfort when responding to questions

The risks of participating in ALDER are minimal. In past research, we have not observed any participants experiencing serious or lasting distress in response to similar interventions or assessments. The intervention has been user-tested to remove any material/content that might be upsetting or insensitive, to reduce the chances of using those questions in future versions. Therefore, the risk of discomfort is extremely low. However, some might experience slight discomfort when asked about their emotions, anxiety, stress, and coping. Participants are notified that they may skip any questions they do not wish to answer. Declining to answer any questions, declining to participate in the study, or declining to continue with the study once enrolled, will not have any impact on a participant's medical care at Northwestern Hospital or any affiliated specialty or primary clinics.

Potential loss of confidentiality in data

The risk of loss of confidentiality is extremely low. Identifiable information will be collected using REDCap which uses industry-standard encryption to protect participants' information while in transit from the moment data is entered to the moment it is stored on HIPAA compliant servers. Data is never fed back to participants or displayed on the participant website. Access to REDCap is granted to key personnel and all study staff handling personally identifiable information will have taken the CITI Human Subjects Training Course. Participants will be assigned and identified by a unique Study ID on the ALDER platform, and their information will be stored in encrypted forms on Northwestern computers. Any hard-copy documents will be stored in locked cabinets in the Department of Medical Social Sciences and all electronic copies of data, study emails, or records will have double-protection through password-protected access for NU servers and REDCap. Even if a participant's account is later compromised, submitted information on the website is protected and not released.

The ALDER online platform is hosted by BrightOutcome and is protected by end-to-end encryption and password measures. Participants will be able to access ALDER intervention on their computer browser or on their mobile phones with an internet connection. Participants will submit their home practice (e.g., gratitude journal) through the website. IRB-approved NU study staff will be able to access the data collected through the platform through direct export. No data will be stored locally on mobile phones nor participants' computers. All data will be collected directly through the website and stored on password-protected, secure NU servers.

Potential loss of confidentiality in general

Once a participant is enrolled in the study, there is the chance someone might see a participant filling out assessments or reading the positive emotion skills on the platform. To protect participant privacy, we encourage participants to be aware of their location (i.e., in a public or crowded space) when completing the online ALDER course and filling out their online assessment. Since the assessments are completed online, this allows for flexibility and participants can answer the questions from the comfort and privacy of their own home on their mobile device/tablet computer/laptop etc.

“Pollyanna”

The risk of proclaiming the importance of positive affect in the stress and coping process is that it may appear to minimize the pain and serious individual and societal consequences associated with major stressful events. We are not advocating a simplistic “don’t worry-be happy” approach nor do we believe that simply increasing positive emotion will prove to be a cure-all for the very real and complex issues facing older adults who are candidates for BZRA deprescribing. Such a Pollyanna-ish stance could easily degenerate into blaming the victim for not thinking the positive thoughts that may prevent depression or other negative consequence of enduring stress. However, we argue that an intervention to increase positive emotions in patients sets the stage for a cascade of adaptive consequences, including reduced burden and improved quality of care. Ultimately, given the high level of comorbidities and lack of mental health care for older adults using BZRAs, we consider increasing positive emotion to be an inherently worthwhile intervention goal.

While our study focuses on positive emotion, we emphasize that ALDER is not a replacement for therapy, nor is it considered a treatment for depression or anxiety. Participants are encouraged to follow the guidelines of their health care clinician and advised that they should not put off starting therapy and/or medication or stop treatments recommended by their health care clinician.

Withdrawal of participants

If a participant wishes to withdraw, they can communicate this on the phone or via email to the project director or other designated study staff. Study staff will also be monitoring communications and potential withdrawal requests coming through on the study website and study email. The participant will then be promptly withdrawn from the study, their data collected and eventually analyzed only up until the point of withdrawal. No further data will be collected after a participant has been withdrawn. We will document the reason for withdrawing. We do not foresee any circumstances under which participants will be withdrawn from the research without their consent.

Possible risk of benzodiazepine withdrawal and worsening of symptoms

Though this study does not involve directly deprescribing BZRAs for patients, there are still standard of care risks for patients who wish to decrease their use of BZRAs, whether or not they choose to participate in ALDER. These risks are especially relevant for Aim 2 participants who may decide, in conjunction with their healthcare clinician, to decrease their use of BZRA medications. Risks include withdrawal symptoms such as gastrointestinal symptoms, tinnitus, sensory hypersensitivity, muscle twitches, perceptual disturbances, hallucinations, depersonalization, cognitive impairment. Research has demonstrated that the risks of symptoms worsening during deprescribing are small and are usually mild and short-term insomnia, anxiety, and restlessness.⁶⁵ Risks will be minimized by weekly monitoring and reporting of elevated withdrawal scores to the prescribing clinician. See the Data Monitoring Plan to Ensure the Safety of Participants below for a detailed description of monitoring procedures.

18.0 Provisions to Protect Participant Privacy and Data Confidentiality:

The research team is committed to the protection of human participants. All study staff will participate in initial training, follow-up training, and ongoing monitoring and supervision to ensure understanding of ethical issues involved in this research. This includes, but is not limited to, the CITI Human Subjects course, training on HIPAA, and measures to protect confidentiality. The research team will also be trained on how to use the REDCap Database, which is encrypted, password-protected, and maintained by the Northwestern University Clinical and Translational Sciences Institute (NUCATS).

The protocol to conduct the focus groups and phone interviews will be followed by study staff in order to protect identifiable information. For example, the study team will conduct the interviews and focus groups in a private room with a closed door, and participants will be advised to participate from a private setting. All audio recordings of focus groups and interviews will be transcribed with all identifying information removed, and the audio recordings will be deleted following transcription.

All data is stored and handled in a confidential manner and will only be stored on HIPAA compliant, password-protected servers accessible to IRB-approved study staff. Participants will not be identified by name on study documents or data shared with outside collaborators. Participants will be assigned and identified by their Study ID and all documents will be held to strict confidentiality and HIPAA compliant standards on encrypted and password protected servers. Confidentiality will be maintained through all phases, including data analysis and publication.

Identifiable information will be collected using REDCap which uses industry-standard encryption to protect participants' information while in transit from the moment data is entered to the moment it is stored on HIPAA compliant servers. Data is never fed back to participants or displayed on the participant website. Access to REDCap is granted to key personnel and all study staff handling personally identifiable information will have taken the CITI Human Subjects Training Course. Participants will be assigned and identified by a unique Study ID on the ALDER platform, and their information will be stored in encrypted forms on Northwestern computers. Any hard-copy documents will be stored in locked cabinets in the Department of Medical Social Sciences and all electronic copies of data, study emails, or records will have double-protection through password-protected access for NU servers and REDCap. Even if a participant's account is later compromised, submitted information on the website is protected and not released.

The ALDER online platform is hosted by BrightOutcome and is protected by end-to-end encryption and password measures. Participants will be able to access ALDER intervention and enter their skills practice (e.g., gratitude journal) on their computer browser or on their mobile phones with an internet connection. IRB-approved NU study staff will be able to access the data collected through the platform through direct export. No data will be stored locally on mobile phones nor participants' computers. All data will be collected directly through the website and stored on password-protected, secure NU servers.

Electronic files and study emails are protected on the departmental server at the Department of Medical Social Sciences. All data remains confidential, and any published results are de-identified. Data will be stored on the password-protected, encrypted server for 7 years after the completion of the study per IRB policy. [name] (Principal Investigator) is the Primary Custodian for the data. The backup to the primary custodian will be statistician [name].

19.0 Data Monitoring Plan to Ensure the Safety of Participants:

We have developed the following data and safety monitoring plan. The pre-formative phase of ALDER will collect data on acceptability of various portions of the intervention.

The interviews, focus groups, assessments, and intervention sessions pose no more than minimal risk to participants. The data and safety-monitoring plan identifies the PI as the primary monitor of risks to human subjects in the form of data and safety related risks. Prompt reporting of serious adverse events will be reported to the institution's IRB and project officer of the funding source by the study PI. Risks, monitoring procedures, and reporting and action plans are described below for both data and safety related risks.

Data Risks and Monitoring

Data related risks. Data related risks to participants could consist of circumstances where an insufficient amount of data was collected to answer the research questions.

Data monitoring procedures. Overall recruitment goals, missing data, and follow-up failures will be monitored by the study director, who will provide regular updates and maintain constant communication with the PI and co-Investigators. Investigators will provide guidance on the study protocol, oversee the process, and adapt the protocol or suggest modifications as needed. The PI, [name], will be the primary data custodian for ALDER.

Data risk reporting and action plan. The backup to the primary custodian, statistician [name], will oversee the data safety and monitoring plan, data management, and data security. She will compile the recruitment numbers during all phases of the study and be responsible for assuring completion of required assessments, maintaining databases, and identifying missing data and missing follow-up assessments. [name] will prepare recruitment and missing data reports for monthly review by the PI. Upon recognition of unacceptable recruitment, follow-up rates, or missing data, the investigators will intervene with strategies to remedy the shortcomings or provide additional monitoring.

Safety Risks and Monitoring

Safety related risks. Safety related risks could consist of:

1. Emotional discomfort while using the ALDER platform
2. Emotional discomfort while completing interviews, focus groups, or assessments
3. Loss of confidentiality in data
4. Loss of confidentiality in general
5. "Pollyanna" effect and mistaking the intervention as therapy
6. Signs of distress or revealing identifying information on the ALDER platform
7. Risk of benzodiazepine withdrawal and worsening symptoms

Safety monitoring procedures. All safety related risks will be monitored routinely throughout the study. [name] will be the main point of contact and the study advisor for questions regarding

safety concerns. She will help the team make recommendations and take research precautions to ensure the safety of our participants. (1-2) It will be made clear to participants that they are allowed to skip any exercises or questions that may cause them emotional distress. Participants are provided instructions on how to use the website, log-in, access the course, and are given the contact information of the Project Director, PI, and the designated study email. Participants can email or call study staff and the study is generally staffed Monday-Friday 9am-5pm except holidays, etc.

Study staff will monitor the website weekly and will be trained to respond immediately to participant needs and/or questions on technology and the platform. There is also a FAQ page on the website for frequently asked questions. If a question is not listed/answered on the FAQ page, participants may call or email study staff. Based on our experience conducting prior trials of online self-guided delivery of positive affect skills (e.g., LEAF, LARKSPUR, MARIGOLD), the study team is well versed in handling/managing instances that might require providing participants with additional resources.

(3) The security of confidential information will be monitored regularly. Participants will be informed that their responses will be kept confidential and not used against them in any legal, medical treatment, or any other manner. (4) Study staff will conduct interviews, focus groups, and other participant calls in a private setting with a closed door for participant confidentiality. Participants are encouraged to participate in a private space and to be mindful of where they complete their online assessments, so as to limit the chance of someone overseeing their answers on their computer/tablet/phone screen.

